19.2. Definitions and Classification

Adverse event definitions are provided in Table 19-1 . Administrative edits were made on the safety definitions from ISO 14155 and EU 2017/745 for clarification purposes.

Table 19-1. Safety Demittions		
Term	Definition	
Adverse Event (AE) Ref: ISO 14155	Any untoward medical occurrence, unintended disease or injury, or any untoward clinical signs (including an abnormal laboratory finding) in subjects, users or other persons, in the context of a clinical investigation, whether or not related to the study medical device and whether anticipated or unanticipated.	
Ref: MEDDEV 2.7/3	NOTE 1 : This includes events related to the study medical device or comparator.	
	NOTE 2 : This definition includes events related to the procedures involved.	
	NOTE 3 : For users or other persons, this definition is restricted to events related to the study medical device.	
Adverse Device Effect (ADE)	Adverse event related to the use of the study medical device	
Ref: ISO 14155 Ref: MEDDEV 2.7/3	NOTE 1 : This includes any adverse event resulting from insufficiencies or inadequacies in the instructions for use, the deployment, the implantation, the installation, the operation, or any malfunction of the study medical device.	
	NOTE 2 : This definition includes any event resulting from use error or from intentional misuse of the study medical device.	
	NOTE 3 : This includes 'comparator' if the comparator is a medical device.	
Serious Adverse Event (SAE)	Adverse event that led to any of the following:	
Ref: ISO 14155 Ref: MEDDEV 2.7/3	 a) death, b) serious deterioration in the health of the subject, users or other persons as defined by either: 	

Table 19-1: Safety Definitions

Term	Table 19-1: Safety Definitions Definition	
Term	1) a life-threatening illness or injury, or	
	 a me-uncatching inness of injury, of a permanent impairment of a body structure or a body function, including chronic diseases, or 	
	3) in-patient hospitalization or prolongation of existing hospitalization, or	
	 4) medical or surgical intervention to prevent life-threatening illness or injury or permanent impairment to a body structure or a body function 	
	c) foetal distress, foetal death, or a congenital abnormality or birth defect including physical or mental impairment.	
	NOTE 1: Planned hospitalization for a pre-existing condition, or a procedure required by the clinical investigational plan, without a serious deterioration in health, is not considered a serious adverse event.	
Serious Adverse Device Effect (SADE)	Adverse device effect that has resulted in any of the consequences characteristic of a serious adverse event.	
Ref: ISO 14155		
Ref: MEDDEV 2.7/3		
Unanticipated Adverse Device Effect (UADE)	Any serious adverse effect on health or safety or any life-threatening problem or death caused by, or associated with, a device, if that effect, problem, or death was not previously identified in nature, severity, or	
Ref: 21 CFR Part 812	degree of incidence in the investigational plan or application (including a supplementary plan or application), or any other unanticipated serious problem associated with a device that relates to the rights, safety, or welfare of subjects.	
Unanticipated Serious Adverse Device Effect (USADE)	Serious adverse device effect which by its nature, incidence, severity, or outcome has not been identified in the current risk assessment.	
Ref: ISO 14155	NOTE 1 : Anticipated serious adverse device effect (ASADE) is an effect which by its nature, incidence, severity or outcome has been identified in the risk assessment.	
Ref: MEDDEV 2.7/3		
Serious Health Threat Ref: ISO 14155	Signal from any adverse event or device deficiency that indicates an imminent risk of death or a serious deterioration in the health in subjects, users or other persons, and that requires prompt remedial action for other subjects, users or other persons.	
·	Note 1 to entry: This would include events that are of significant and unexpected nature such that they become alarming as a potential serious health hazard or possibility of multiple deaths occurring at short intervals.	
Device Deficiency	An inadequacy of a medical device related to its identity, quality, durability, reliability, usability, safety or performance.	
Ref: ISO 14155	NOTE 1 : Device deficiencies include malfunctions, use errors, and inadequacy in the information supplied by the manufacturer including	
Ref: MEDDEV 2.7/3	labelling.NOTE 2: This definition includes device deficiencies related to the investigational medical device or the comparator.	

Table 19-1: Safety Definitions

Form/Template 92120219_Rev/Ver D LUX-Dx PERFORM Protocol, 92557593, Rev/Ver C Page 51 of 66

Term	Definition		
The following definitions will be classification purposes:	used for defining hospitalization or prolongation of hospitalization for SAE		
Hospitalizations	Hospitalization does not include:		
	• emergency room visit that does not result in in-patient admission		
	Note: although an emergency room visit does not itself meet the definition for hospitalization, it may meet other serious criteria (e.g. medical or surgical intervention to prevent permanent impairment or damage)		
	• elective and pre-planned treatment/surgery for a pre-existing condition that is documented in the subject's record at the time of consent/enrollment		
	• admission for social reasons and/or respite care in the absence of any deterioration in the subject's general condition (e.g. subject is homeless, caregiver relief)		
	 pre-planned, protocol-specified admission related to the clinical study (e.g. procedure required by protocol) 		
Prolongation of hospitalization			
	Note: new adverse events occurring during the hospitalization are evaluated to determine if they prolonged hospitalization or meet another SAE criteria.		

Table 19-1: Safety Definitions

19.3. *Relationship to Device(s)*

An Investigator must assess the relationship of the reportable AE to the device and/or implant procedure. See criteria in Table 19-2:

Classification	Description
Not Related	Relationship to the device, comparator, or procedures can be excluded when:
Ref: MEDDEV 2.7/3	- the event is not a known side effect of the product category the device belongs to or of similar devices and procedures;
	- the event has no temporal relationship with the use of the study device or the procedures;
	- the serious event does not follow a known response pattern to the medical device (if the response pattern is previously known) and is biologically implausible;
	- the discontinuation of medical device application or the reduction of the level of activation/exposure - when clinically feasible – and reintroduction of its use (or increase of the level of activation/exposure), do not impact on the serious event;
	- the event involves a body-site or an organ not expected to be affected by the device or procedure;
	- the serious event can be attributed to another cause (e.g. an underlying
	or concurrent illness/ clinical condition, an effect of another device, drug, treatment or other risk factors);
	- the event does not depend on a false result given by the study device used for diagnosis, when applicable; harms to the subject are not clearly due to use error;
	- In order to establish the non-relatedness, not all the criteria listed above might be met at the same time, depending on the type of device/procedures and the serious event.
Possibly Related Ref: MEDDEV 2.7/3	The relationship with the use of the study device or comparator, or the relationship with procedures is weak but cannot be ruled out completely. Alternative causes are also possible (e.g. an underlying or concurrent illness/ clinical condition or/and an effect of another device, drug or treatment). Cases were relatedness cannot be assessed or no information has been obtained should also be classified as possible.
Probably Related Ref: MEDDEV 2.7/3	The relationship with the use of the study device or comparator, or the relationship with procedures seems relevant and/or the event cannot be reasonably explained by another cause, but additional information may be obtained.

Table 19-2: Criteria for Assessing Relationship of Study Device or Procedure to Adverse Event

Classification	Description
Causal Relationship Ref: MEDDEV 2.7/3	The serious event is associated with the study device, comparator, or with procedures beyond reasonable doubt when:
5	- the event is a known side effect of the product category the device belongs to or of similar devices and procedures;
	- the event has a temporal relationship with the study device use/application or procedures;
	- the event involves a body-site or organ that
	-the study device or procedures are applied to;
	-the study device or procedures have an effect on;
	- the serious event follows a known response pattern to the medical device (if the response pattern is previously known);
	- the discontinuation of medical device application (or reduction of the level of activation/exposure) and reintroduction of its use (or increase of the level of activation/exposure), impact on the serious event (when clinically feasible);
	- other possible causes (e.g. an underlying or concurrent illness/ clinical condition or/and an effect of another device, drug or treatment) have been adequately ruled out;
	- harm to the subject is due to error in use;
	- the event depends on a false result given by the study device used for diagnosis, when applicable;
	- In order to establish the relatedness, not all the criteria listed above might be met at the same time, depending on the type of device/procedures and the serious event.

Table 19-2: Criteria for Assessing Relationship of Study Device or Procedure toAdverse Event

19.4. Investigator Reporting Requirements

The communication requirements for reporting to BSC are as shown in Table 19-3. Adverse events must always be reported through the EDC system whenever possible. However, in the case of any issues where alternative methods of reporting is necessary (i.e. the EDC system is not available), the investigator should contact Boston Scientific and provide the relevant adverse event information in a timely manner by using the study-specific safety mailbox: [contact].

Event Classification	Communication Method	Communication Timeline post-market studies* (MEDDEV 2.12/1: GUIDELINES ON A MEDICAL DEVICE VIGILANCE SYSTEM)
Serious Health Threat	Complete applicable eCRF/paper form with all available new and updated information.	 Within 1 business day of first becoming aware of the event. Terminating at the end of the study.

Form/Template 92120219_Rev/Ver D LUX-Dx PERFORM Protocol, 92557593, Rev/Ver C

	1	Page 54 of 66
Event Classification	Communication Method	Communication Timeline post-market studies* (MEDDEV 2.12/1: GUIDELINES ON A MEDICAL DEVICE VIGILANCE SYSTEM)
	Provide all relevant source documentation (de-identified/ pseudonymized) for reported event.	• Upon request of sponsor.
Unanticipated Adverse Device Effect / Unanticipated Serious Adverse Device Effect	Complete AE CRF page with all available new and updated information.	 Within 1 business day of first becoming aware of the event Reporting required through end of study
	Provide all relevant source documentation (de-identified/ pseudonymized) for reported event.	• Upon request of sponsor.
Serious Adverse Event	Complete AE CRF page with all available new and updated information.	 Within 3 calendar days after becoming aware of the event or as per local/regional regulations. Reporting required through end of study
	Provide all relevant source documentation (de-identified/ pseudonymized) for reported event.	 When documentation is available Upon request of sponsor.
Serious Adverse Device Effects	Complete AE CRF page with all available new and updated information.	 Within 3 calendar days of first becoming aware of the event or as per local/regional regulations. Reporting required through end of study
	Provide all relevant source documentation (de-identified/ pseudonymized) for reported event.	When documentation is availableUpon request of sponsor.
Device Deficiencies (including but not limited to failures, malfunctions, and product nonconformities) Note: Any Device Deficiency that might have led to a serious adverse event if a) suitable action had not been taken or b) intervention had not been made or c) if circumstances had been less fortunate is considered a reportable event.	Complete Device Deficiency CRF with all available new and updated information.	 Within 3 calendar days of first becoming aware of the event. Reporting required through end of study

 $P_{age} 5/$ of 66

Form/Template 92120219 Rev/Ver D Confidential LUX-Dx PERFORM Protocol, 92557593, Rev/Ver C Page 55 of 66 **Communication Timeline post-market Event Classification Communication Method** studies* (MEDDEV 2.12/1: **GUIDELINES ON A MEDICAL DEVICE** VIGILANCE SYSTEM) Provide all relevant source • Upon request of sponsor documentation (de-identified/ pseudonymized) for reported event. Complete AE CRF page, Adverse Event including • Within 10 business days after becoming Adverse Device Effects which contains such aware of the information. information as date of AE. Reporting required through end of study treatment of AE resolution, assessment of seriousness and relationship to the device. Provide all relevant source Upon request of sponsor • documentation (deidentified/ pseudonymized) for reported event.

19.5. Boston Scientific Device Deficiencies

Device deficiencies will be documented and reported to BSC. If possible, the device(s) should be returned to BSC for analysis. Instructions for returning the device(s) will be provided to the study site in the event of an ICM explant during study participation. Device deficiencies should also be documented in the subject's source records.

Device deficiencies are not adverse events. However, an adverse event that results from a device deficiency, would be recorded as an adverse event on the appropriate CRF.

19.6. Reporting to Regulatory Authorities/ IRBs/ ECs/ REBs/ Investigators

BSC is responsible for reporting adverse event information to all participating Principal Investigators, IRBs/ECs and regulatory authorities, as applicable.

The PI is responsible for informing the IRB/EC and regulatory authorities of UADEs and SAEs as required by local/regional regulations.

19.7. Subject Death Reporting

A subject death during the study must be reported to Boston Scientific as soon as possible and, in any event, within three (3) calendar days of center aware date. The center's IRB/EC must be notified of any deaths in accordance with that center's IRB/EC policies and procedures. Whenever possible, the device should be interrogated and BSC system components (e.g., the device) should be removed intact and returned promptly to BSC RM for analysis.

Form/Template 92120219_Rev/Ver D LUX-Dx PERFORM Protocol, 92557593, Rev/Ver C Page 56 of 66

A detailed narrative (death letter) that provides detailed information describing the circumstances surrounding the death may be requested. A death narrative in the local language is acceptable, if accompanied by a translation in English. The details listed below should be addressed in the death narrative in order for BSC to understand the circumstance surrounding the death:

- Date and time of death;
- Place death occurred;
- Immediate cause of death;
- Rhythm at the time of death, if known (include any available documentation);
- Whether or not the death was witnessed;
- Any other circumstances surrounding the death;
- Approximate time interval from the initiating event to death (temporal course) items to consider include, but are not limited to: information regarding last time subject was seen by investigator, last office visit, etc.
- Investigator or sub-Investigator signature and date.

Other Source documents may be requested by BSC. BSC Safety representatives will review, at minimum, information regarding subject deaths that are related to ICM system or implant procedure.

20. Informed Consent

Subject participation in this clinical study is voluntary. Informed Consent is required from each subject. The Investigator is responsible for ensuring that Informed Consent is obtained prior to the use of any study devices, study-required procedures and/or testing, or data collection.

The obtaining and documentation of Informed Consent must be in accordance with the principles of the Declaration of Helsinki, ISO 14155, any applicable national regulations, and local Ethics Committee and/or Regulatory authority, as applicable. The ICF must be accepted by BSC or its delegate (e.g. CRO) and approved by the site's IRB/EC, or central IRB/central EC, if applicable.

Boston Scientific will provide a study-specific template of the ICF to investigators participating in this study. The ICF template may be modified to meet the requirements of the investigative site's IRB/EC. Any modification requires acceptance from BSC prior to use of the form. The ICF must be in a language understandable to the subject and if needed, BSC will assist the site in obtaining a written consent translation. Translated consent forms must also have IRB/EC approval prior to their use. Privacy language shall be included in the body of the form or as a separate form as applicable.

The process of obtaining Informed Consent shall at a minimum include the following steps, as well as any other steps required by applicable laws, rules, regulations and guidelines:

• be conducted by the PI or designee authorized to conduct the process,

- include a description of all aspects of the clinical study that are relevant to the subject's decision to participate throughout the clinical study,
- avoid any coercion of or undue influence of subjects to participate,
- not waive or appear to waive subject's legal rights,
- use native language that is non-technical and understandable to the subject or his/her legal representative,
- provide ample time for the subject to consider participation and ask questions if necessary,
- ensure important new information is provided to new and existing subjects throughout the clinical study.

The ICF shall always be signed and personally dated by the subject and by the investigator and/or an authorized designee responsible for conducting the informed consent process. The original signed ICF will be retained by the site and a copy of the signed and dated document and any other written information must be given to the subject.

Failure to obtain subject consent will be reported by BSC to the applicable regulatory authority according to their requirements (e.g., FDA requirement is within 5 working days of learning of such an event). Any violations of the informed consent process must be reported as deviations to the sponsor and local regulatory authorities (e.g. IRB/EC), as appropriate.

If new information becomes available that can significantly affect a subject's future health and medical care, that information shall be provided to the affected subject(s) in written form via a revised ICF or, in some situations, enrolled subjects may be requested to sign and date an addendum to the ICF. In addition to new significant information during the course of a study, other situations may necessitate revision of the ICF, such as if there are amendments to the applicable laws, protocol, a change in Principal Investigator, administrative changes, or following annual review by the IRB/EC. The new version of the ICF must be approved by the IRB/EC. Acceptance by Boston Scientific is required if changes to the revised ICF are requested by the site's IRB/EC. The IRB/EC will determine the subject population to be re-consented.

21. Committees

21.1. Safety Monitoring Process

The BSC personnel from the Medical Safety and Safety Trial Operation group review safety data as it is reported by the sites throughout the duration of the study. During scheduled monitoring activities, clinical research monitors further support this review through their review of source documents and other data information. The BSC Medical Safety and Safety Trial Operations team include medical professionals with expertise in electrophysiology and with the necessary therapeutic and subject matter expertise to evaluate and classify the events into the categories outlined above.

21.2. Steering Committee

A Steering Committee composed of study's Coordinating Principal Investigator(s) and physicians with expertise in ICM technology will be convened. Responsibilities may include oversight of the overall conduct of the study with regard to protocol development, study progress, subject safety, overall data quality and integrity, and first line review and final decision making of independent medical reviewer recommendations, as well as disseminating any study results through appropriate scientific sessions and publications.

Steering Committee members may participate in the review and approval of all requests for data analysis, abstract and manuscript preparation, and submission.

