7.3. Justification for the Study Design

The objective of the LUX-Dx PERFORM Study is to collect data in a clinical setting reflecting real-world usage of the LUX-Dx ICM. Therefore, a prospectively enrolled, observational, post-market study design was determined to be appropriate. Subject enrollment requirements are supported by the following:

- A sample size of 227 subjects will be required to power the first primary safety endpoint analysis (acute endpoint), and 226 subjects will be required to power the second primary safety endpoint (chronic endpoint).
- The Holter study group is expected to enroll approximately 600 subjects, including approximately 300 subjects from the "AF management, Post-AF ablation, or Suspected AF" subgroup, and approximately 300 subjects from the other 2 subgroups ("Syncope" and "Cryptogenic stroke"). The distribution of the device indications is desired to generate at least 100 subjects with a detected AF episode during the Holter

	Form/Template 92120219_Rev/Ver D			
Confidential	LUX-Dx PERFORM Protocol, 92557593, Rev/Ver C			
	Page 25 of 66			
monitoring period. Refer to Section 11.1.2.2 for rationales of the sample size				

requirement in the Holter study.

Refer to Section 11 for details of overall study sample size discussion.

8. Subject Selection

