11.1.3.2. Statistical Methods

The ICM system-related complication-free rate at 30 days post-implant will be calculated using Kaplan-Meier methodology. The 97.5% one-side lower pointwise confidence limit of

	Form/Template 92120219_Rev/Ver D
Confidential	LUX-Dx PERFORM Protocol, 92557593, Rev/Ver C
	Page 38 of 66

the ICM system-related complication-free rate will be calculated via log-log methodology and compared to the performance target of 94%. If the lower confidence limit exceeds 94% then the null hypothesis will be rejected.

The adjudication of the ICM system-related adverse events and complications will be conducted by independent physician reviewer(s).

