21.3. Independent Medical Reviewers – Arrhythmia Episodes

An independent group of physician(s) with pertinent expertise will be established for the study. Their responsibility includes reviewing and adjudicating the arrhythmia episodes detected and recorded by the LUX-Dx ICM.

The group will include practitioners of electrophysiology (EP), cardiac device implant, as well as experts with the necessary therapeutic and subject matter expertise to adjudicate the arrhythmia episodes outlined above. Responsibilities, qualifications and procedures are outlined in a charter.

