21.4. Independent Medical Reviewers – Safety Endpoints

An independent medical review, performed by at least one individual with pertinent expertise, will be performed to review serious adverse events reported by study investigators for adjudication of LUX-Dx ICM system-related complications. The independent medical review will consist of a review of a safety event dossier, which may include copies of subject source documents provided by study sites, for all reported subject death from any cause.

An independent medical reviewer may be a practitioner of EP and/or cardiology or an expert with the necessary therapeutic and subject matter expertise to adjudicate the ICM system-related complications. Responsibilities, qualifications and procedures are outlined in a charter.

22. Suspension or Termination

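### Section 21.2 lets a Steering Committee that includes the coordinating investigator(s) take the final decision on independent reviewers' recommendations, so independent adjudication of the two primary safety endpoints is not assured

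*Combined protocol and SAP*

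**What the plan says.** - **Section 11.1.3.2** (statistical methods, acute endpoint) commits adjudication of system-related adverse events and complications to independent physicians. The corresponding chronic section, 11.1.4.2, does not repeat this.
- **Section 21.4** provides an independent medical review by at least one qualified person, which "will be performed to review serious adverse events reported by study investigators for adjudication of LUX-Dx ICM system-related complications". On process it says only that "Responsibilities, qualifications and procedures are outlined in a charter".
- **Section 21.3** makes a separate independent physician group responsible for "reviewing and adjudicating the arrhythmia episodes detected and recorded by the LUX-Dx ICM", also under a charter.
- **Section 21.2** describes a Steering Committee "composed of study's Coordinating Principal Investigator(s) and physicians with expertise in ICM technology". Its list of duties opens permissively ("Responsibilities may include oversight of the overall conduct of the study") and goes on to include "first line review and final decision making of independent medical reviewer recommendations". No independence requirement is stated for its members.

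**The concern.** Sections 11.1.3.2, 21.3 and 21.4 say who adjudicates. They do not say whose decision stands. Section 21.2 is the only supplied text on final authority over the reviewers' output, and it names a committee that includes the coordinating investigator(s).

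If *recommendations* covers event classifications, that committee may decide whether an event counts as a system-related complication. Each primary safety conclusion compares one lower confidence limit with a fixed goal, with no control arm in which a shift in classification could cancel out. A lenient final decision would move the result in one direction only. The same clause also reaches the arrhythmia adjudications of Section 21.3, which bear on primary effectiveness objective 2, although that objective has no formal hypothesis.

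**Working it through.** **Reading the sections together**

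1. Who are the independent medical reviewers? Only two groups are described, in Sections 21.3 and 21.4.
2. What do they produce? The only task given to either group is review for adjudication: arrhythmia episodes in one case, serious adverse events and death dossiers in the other. Ongoing review of safety data belongs to sponsor personnel (Section 21.1). No conduct-advice role is described for the independent reviewers.
3. So the recommendations in Section 21.2 can be read as their adjudications. A narrower reading, general advice on conduct or safety, is also possible because the term is undefined.
4. Does any supplied text exempt the classification from the committee, or call it final or locked? No.

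**How sensitive the tests are to one classification**

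The sample sizes 227 (acute) and 226 (chronic) come from Section 7.3. They cannot be re-derived, because the supplied text does not show the assumed rates and power; they are not in dispute. The goals (94%, 93%) and the one-sided 97.5% log-log Kaplan-Meier limit come from Sections 11.1.3 and 11.1.4. Assumption: no censoring, so with *d* subjects having an event among *n*:

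- S = 1 − d/n
- Greenwood standard error of log S = √[d / (n(n − d))]
- standard error on the log-log scale: v = √[d / (n(n − d))] / |log S|
- lower limit = S^exp(1.96 v)

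For d = 6, n = 227: S = 221/227 = 0.97357; v = 0.01094/0.02679 = 0.4083; exp(1.96 × 0.4083) = 2.226; lower limit = 0.97357^2.226 = 0.9421.

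| Endpoint | n | Goal | Events | S | Lower limit | Result |
|---|---|---|---|---|---|---|
| Acute | 227 | 94% | 6 | 97.36% | 94.21% | pass |
| Acute | 227 | 94% | 7 | 96.92% | 93.64% | fail |
| Chronic | 226 | 93% | 8 | 96.46% | 93.05% | pass |
| Chronic | 226 | 93% | 9 | 96.02% | 92.49% | fail |

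False-pass probability with the true rate exactly at the goal (exact binomial), first as planned and then if one event per study were always moved to unrelated:

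- Acute: P(X ≤ 6 | 227, 0.06) = 0.0155; P(X ≤ 7) = 0.0348.
- Chronic: P(X ≤ 8 | 226, 0.07) = 0.0207; P(X ≤ 9) = 0.0418.

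Both shifted values exceed the nominal 0.025.

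**How often a study would sit at the boundary**

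- At the goal, expected events are 227 × 0.06 = 13.6 and 226 × 0.07 = 15.8. One change would not alter a typical result. The chance of exactly 7 acute events is 0.0348 − 0.0155 = 1.9%; of exactly 9 chronic events, 0.0418 − 0.0207 = 2.1%.
- The true rates expected are not in the supplied text. Assuming a range of 97% to 98%, the chance of exactly 7 acute events is 15% down to 8%, and of exactly 9 chronic events 10% down to 2%.

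**The case against.** The strongest reply has four parts.

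1. *The specific text should prevail.* Sections 11.1.3.2 and 21.4 state firmly that independent reviewers adjudicate, while Section 21.2 only lists what committee duties may be. The vocabulary also differs: Sections 21.3 and 21.4 speak of adjudication, Section 21.2 of recommendations, in a sentence about overall oversight. This stands as a reason to treat the point as an unresolved conflict and not as proof that the committee will override anyone. It does not remove the conflict, because the firm statements are silent on finality and the reviewers are given no task other than review for adjudication.
2. *The charters may settle it.* They may, and they were not supplied. A charter that makes the reviewers' classification final would still have to be reconciled with Section 21.2.
3. *Section 11.3.5 requires changes to planned analyses to be documented.* That governs changes to statistical methods. It does not say who finalises an event classification.
4. *The numbers are hypothetical.* This is correct. Any threshold test reverses at its boundary, and the error rates assume one downward change in every study. They describe sensitivity and are not evidence that reclassification would happen. The finding rests on the wording.

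**Conclusion.** The concern holds as a conflict within the protocol. Section 21.2 permits a committee containing the coordinating investigator(s) to take the final decision on independent reviewers' recommendations, and the supplied text does not assure independent final classification for either primary safety endpoint.

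At the boundary a single event decides each test. A consistent one-event shift would roughly double the false-pass probability, to 3.5% (acute) and 4.2% (chronic). This assumes no censoring, analysis of 227 and 226 subjects, and one downward reclassification per study; the number and direction of changes are assumptions. Confidence is medium, because *recommendations* is undefined and the charters are unseen. It should be fixed, since the change protects two primary single-arm tests at very little cost.

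**What to change.** - **Section 21.2:** limit the clause to recommendations on study conduct and safety oversight, and say that it excludes event classification; or strike it.
- **Section 21.4:** state that the independent reviewers' classification of system-related complications is final for analysis of both the acute and the chronic endpoint, and is locked before the analysis is run.
- **Section 21.3:** say the same for arrhythmia episodes.
- **Both charters:** align them with this wording.

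The cost is protocol and charter wording only, with no added subjects, procedures or staff. If independent finality is already intended, the edit simply records it.
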